## ABBREVIATIONS AND DEFINITIONS OF TERMS

°C	Degrees centigrade
AE	Adverse event
AF	Atrial Fibrillation
ALT	Alanine aminotransferase
AST	Aspartate aminotransferase
aPTT	Activated Partial Thromboplastin Time
BMS	Bristol-Myers Squibb
CMP	Complete metabolic panel
CBC	Complete blood count
CK	Creatine kinase
CMB	Cerebral Microbleeds
CT	Computed Tomography
DSMB	Data and Safety Monitoring Board
E.G.	For Example
EKG	Electrocardiogram
EOS	End of Study
EW	Early Withdrawal
FDA	Food and Drug Administration
GRE	Gradient Recovery Echo
INR	International Normalization Ratio
IRB	Institutional Review Board
LAR	Legally Authorized Representative
MRI	Magnetic Resonance Imaging
mRS	Modified Rankin Scale
NIHSS	National Institute of Health Stroke Scale
NVAF	Non-Valvular Atrial Fibrillation
NSAE	Non Serious Adverse Event
PI	Principal Investigator
SS-QOL	Stroke Specific Quality of Life Scale
SACCO	Stroke Adjudication Committee for Classification and Organization
SWI	Susceptibility Weighted Imaging
TEE	Trans-Esophageal Echocardiogram
TSH	Thyroid Stimulating Hormone
TIA	Transient Ischemic Attack
ULNS	Upper Limit of Normal
USF	University of South Florida
WOCBP	Women of Child Bearing Potential

## Schedule of Study Procedures

TIA -Apixaban group	Screen/ Baseline	Treatment Initiation	Maintenance ‡						End of Study	30day PC	Early Withdrawal	Unsch
			3	4	5	6	7	8				
Visit Number	1	2	3	4	5	6	7	8	9	10		
Study Days (Visit Window)	0	$\beta$ (See also table 2)	14 ( $\pm 3$ )	30 ( $\pm 5$ )	60 ( $\pm 10$ ) )	90 ( $\pm 10$ ) )	120 ( $\pm 10$ ) )	150 ( $\pm 10$ ) )	180 ( $\pm 10$ )	210 ( $\pm 10$ ) )		
Informed Consent	✓											
Inclusion/Exclusion Criteria	✓											
General Medical History/Demographics	✓											
Physical Exam	✓		✓	✓	✓	✓	✓	✓	✓		✓	✓
Vital Signs §	✓		✓	✓	✓	✓	✓	✓	✓		✓	✓
mRS	✓		✓	✓	✓	✓	✓	✓	✓		✓	
NIHSS	✓		✓	✓	✓	✓	✓	✓	✓		✓	✓
SS-QOL	✓			✓					✓		✓	✓
Urine pregnancy test †	✓	✓ †	✓	✓	✓	✓	✓	✓	✓		✓	
12-lead ECG	✓		✓	✓	✓	✓	✓	✓	✓		✓	✓
Clinical Lab Evaluation*	✓ **			✓		✓			✓		✓	✓
PT/INR ( Warfarin arm only)		✓	✓	✓	✓	✓	✓	✓	✓		✓	✓
TEE	✓ †											
Event Monitor (prior to DC)		✓										
Carotid Ultrasound	✓											
MRI or CT scan	✓		✓						✓		✓	
Record AE/SAEs		✓	✓	✓	✓	✓	✓	✓	✓	✓	✓	✓
Prior and con. medications/procedures	✓	✓	✓	✓	✓	✓	✓	✓	✓	✓	✓	
Dispense Study Drug		✓	✓	✓	✓	✓	✓	✓				✓
Drug Compliance			✓	✓	✓	✓	✓	✓	✓		✓	✓
Non-study anticoagulation initiation									✓		✓	

$\beta$  drug initiation will be as follows: TIA: Apixaban arm day 0-3/Warfarin arm day 7( $\pm 5$ ): Small stroke: Apixaban arm day 3-5/Warfarin arm day 14( $\pm 5$ ): Medium stroke: Apixaban arm day 7-9/Warfarin arm day 14( $\pm 5$ )

\* Results of existing tests will be obtained from subject's hospital chart to assess eligibility. If tests results are not available labs will be performed at the visit. See section 6 for a detailed description of what this entails.

§ Vitals: BP, HR,, weight, (RR and Temperature are optional, height obtained at baseline only)

\*\* Labs for inclusion/exclusion criteria will include CMP, CBC with diff and platelets, Creatinine, PT/INR, LFTs and Lipid panel.

† performed prior to discharge

† All WOCBP MUST have a negative pregnancy test within 24 hours before receiving apixaban. The minimum sensitivity of the pregnancy test must be 25 IU/L or equivalent units of HCG. If the pregnancy test is positive, the subject must not receive apixaban and must not be enrolled in the study. † Study day at screening is day of event

Dosing Category	Apixaban dose initiation window
TIA	Day 0-3
Small Stroke	Day 3-5
Medium Stroke	Day 7-9
Dosing Category	Warfarin dose initiation window
TIA	Day 7 (+/- 5)
Small Stroke	Day 14 (+/- 5)
Medium Stroke	Day 14 (+/- 5)

Table 2

## 1 BACKGROUND INFORMATION AND RATIONALE

### 1.1 Introduction

Non-Valvular Atrial Fibrillation (NVAF) is a growing problem with prevalence in the United States of approximately 5 million, up to half of whom are unaware that they have the most common cardiac arrhythmia. Patients with AF are at five times greater risk for having a stroke than those in normal sinus rhythm. Current clinical practice prohibits early use of anticoagulation following stroke even when etiology is suspected as embolic. Furthermore, strokes in patients with atrial fibrillation have been shown to be associated with increased morbidity and mortality.

Several recent trials with novel anticoagulation (table 3) have shown stroke prevention efficacy equal to or superior to warfarin with over a fifty percent reduction in intracranial bleed; however they excluded subjects with a stroke within seven or less days.

The results from these pivotal trials are listed below:

	Rely		Rocket AF		Aristotle		Engage AF	
	Warfarin	Dabigatran 150mg	Warfarin	Rivaroxaban	Warfarin	Apixaban	Warfarin	Edoxaban 60mg
Stroke Per year	1.69 %	1.11%	2.2 %	1.7%	1.6%	1.27%	1.50 %	1.18%
Hemorrhagic stroke per year	0.38%	0.10%	0.7 %	0.5 %	0.47%	0.24%	0.47%	0.26%
Major Bleed Per year	3.36 %	3.11 %	14.5% *	14.9% *	2.09%	2.13%	3.43 %	2.75 %
Intracranial Bleed Per Year	0.74%	0.30%	0.70 %	0.50 %	0.80 %.	0.33 %	0.85 %	0.39 %

Table3\* total bleed rate accounted for not just major bleed

This study is being conducted to evaluate if anticoagulation treatment with Apixaban, initiated earlier than the recommended guidelines of within 14 days after embolic stroke for patients with atrial fibrillation is associated with decreased risk for recurrent embolic stroke without increasing the risk of hemorrhagic transformation compared to conventional treatment (i.e. no anticoagulation treatment within 14 days of stroke).

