### **3 STUDY OBJECTIVES**

#### **3.1 Research Hypothesis**

Early anticoagulation treatment regimen with Apixaban at 0-3 days after TIA, 3-5 days after small ischemic stroke and 7 to 9days after medium ischemic stroke for patients with atrial fibrillation will result in a decreased incidence for recurrent ischemic stroke and without significant increase in risk of intracranial hemorrhage compared to conventional treatment for TIA, small and medium sized strokes.

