#### **3.2 Primary Objective**

In patients with atrial fibrillation with recent cerebral ischemic symptoms (0-48 hours), to evaluate whether the treatment regimen with Apixaban (Three subgroups: TIA: day 0-3; small stroke: day 3-5; medium stroke: day 7-9) compared with standard of care treatment regimen with warfarin (Three subgroups: TIA: day 7±5; Small or medium stroke: day 14±5) reduces the composite endpoint of fatal stroke, recurrent ischemic stroke or TIA at 30 and 180 days. (See figure 1)

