#### 4 INVESTIGATIONAL PLAN

##### 4.1 General Schema of Study Design

This will be a multi-center, open label, randomized, active control, parallel-group pilot trial to examine the effect of initiation of APIXABAN at days 0-3 (TIA), days 3-5 (small stroke) and days 7-9 (medium stroke) to decrease fatal and/or recurrent stroke/TIA in 120 subjects who have suffered a recent (0 to 48 hours from symptoms) TIA, or small to medium ischemic stroke as defined by appendix 13.1 compared to standard of care warfarin treatment regimen. Subjects will be randomly assigned in a 1:1 ratio to one of two treatment arms (apixaban or warfarin). Subjects will be followed for a total of 180 days from screening through follow-up.

[figure not shown]

Figure 1

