### **7 STUDY ENDPOINTS AND EVALUATIONS**

#### **7.1 Primary Endpoint**

Endpoint data will start at randomization up to 180 days. These composite endpoints include:

- Fatal stroke
- Recurrent Ischemic stroke
- New hemorrhagic stroke

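### Early start comes only with apixaban, so the 30- and 180-day contrasts support conclusions about the combined regimen, not about earlier start as section 1.1 words it

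*Combined protocol and SAP*

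**What the plan says.** - **Aim in 1.1.** The study is to show whether apixaban "initiated earlier than the recommended guidelines of within 14 days after embolic stroke for patients with atrial fibrillation is associated with decreased risk" of recurrent embolic stroke. The same sentence defines the comparator as no anticoagulation during the first 14 days.
- **Hypothesis and objectives, 3.1-3.3.** Section 3.1 expects that an early apixaban regimen "will result in a decreased incidence for recurrent ischemic stroke and without significant increase in risk of intracranial hemorrhage" compared with conventional treatment. Sections 3.2 and 3.3 compare one treatment regimen with another.
- **Arms.** Section 4.1 has two arms, allocated 1:1. Section 3.2 starts apixaban at "TIA: day 0-3; small stroke: day 3-5; medium stroke: day 7-9" and warfarin at "TIA: day 7±5; Small or medium stroke: day 14±5". There is no early-warfarin arm and no later-apixaban arm.
- **Clock.** Section 7.1: "Endpoint data will start at randomization up to 180 days". Section 4.1: "Subjects will be followed for a total of 180 days from screening through follow-up".
- **Analysis.** Section 8.1.2 fits a logistic model with six arm-by-stratum groups and contrasts all apixaban groups with all warfarin groups, for events by 30 and by 180 days. Section 8.1.3 does much the same for intracranial hemorrhage, with one-sided tests.
- **Imaging.** Sections 5.5 and 7.2 schedule scans at day 14 and at the end of study.
- **Prior evidence on the drugs.** Section 1.1 describes the newer agents as "equal to or superior to warfarin with over a fifty percent reduction in intracranial bleed", in trials that excluded recent stroke.

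**The concern.** The contrast named in 1.1, anticoagulated against not yet anticoagulated, exists only until the control arm starts warfarin. After that the trial compares two drugs. Section 1.1 itself reports that these drugs differ in stroke and intracranial bleeding, with no reference to an early start. A cumulative count at 30 or 180 days adds the two periods together, and no arm or model term separates them.

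The safety aim is the more exposed. The worry about early anticoagulation is early intracranial bleeding. If apixaban causes fewer bleeds than warfarin over the following months, a cumulative count leans towards finding no excess. Section 8.1.5 says the pilot is meant to inform larger studies, and these would inherit any misattribution to start time.

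**Working it through.** **Inputs.** Start windows from Table 2 and section 3.2. Follow-up of 180 days from 4.1. Annual rates from Table 3 for the apixaban-versus-warfarin trial: stroke 1.27% vs 1.6%, intracranial bleed 0.33% vs 0.80%. Sixty patients per arm (120 split 1:1). The plan gives no figure of its own for the share of follow-up.

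**Step 1. How the 180 days divide**, with apixaban at its window midpoint and warfarin at its nominal day:

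| Stratum | Neither arm on drug | Apixaban vs nothing | Both on drug |
|---|---|---|---|
| TIA | 1.5 d (0.8%) | 7 - 1.5 = 5.5 d (3.1%) | 180 - 7 = 173 d (96.1%) |
| Small stroke | 4 d (2.2%) | 14 - 4 = 10 d (5.6%) | 180 - 14 = 166 d (92.2%) |
| Medium stroke | 8 d (4.4%) | 14 - 8 = 6 d (3.3%) | 166 d (92.2%) |

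Across the warfarin windows the last column runs as follows:
- TIA (start day 2-12): 168/180 to 178/180, or 93.3-98.9%.
- Stroke (start day 9-19): 161/180 to 171/180, or 89.4-95.0%.

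Warfarin is counted here from its first dose. Section 5.2 adds INR checks until 2.0-3.0 is reached but gives no time to range. Counted from therapeutic INR, the shares would be lower.

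**Step 2. The 30-day reading.** Both arms are on drug for 23/30 = 76.7% (TIA) and 16/30 = 53.3% (stroke) of the time, so this reading is mixed too.

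**Step 3. Drug-only difference at Table 3 rates.** The formula is rate difference x days/365.25, over 166 to 180 days.
- Stroke: ratio 1.27/1.6 = 0.79. Difference 0.33 x 166/365.25 = 0.15 points, to 0.33 x 180/365.25 = 0.16 points. Times 60: about 0.09-0.10 patient.
- Intracranial bleed: ratio 0.33/0.80 = 0.41. Difference 0.47 x 166/365.25 = 0.21 points, to 0.47 x 180/365.25 = 0.23 points. Times 60: about 0.13-0.14 patient.

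**Step 4. Masking, with assumed early risks.** Suppose early start doubles early intracranial bleeding from 1% to 2%. Over 166 later days at Table 3 rates, warfarin adds 0.80 x 166/365.25 = 0.36% and apixaban 0.33 x 166/365.25 = 0.15%. The totals are 2.15% vs 1.36%, so 0.79 of the 1.00-point excess remains. Complete cancellation needs a later warfarin risk x with 1 + x = 2 + 0.4125x. That gives x = 1/0.5875 = 1.70%, about 4.7 times the Table 3 figure (1.70/0.36).

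**Step 5. What an early window would contain.** Up to nominal warfarin start, the arms differ in being on drug for 5.5/7 = 79% of the time (TIA), 10/14 = 71% (small stroke) and 6/14 = 43% (medium stroke).

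**The case against.** Several counter-arguments stand, in whole or in part.

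- **Regimen wording.** Section 3.1 names the drug, the timing and the word regimen, and 3.2 and 3.3 ask an answerable regimen question. The sentence in 1.1 also names apixaban just before the words quoted. A reader might infer that the objectives as a whole overclaim. They do not; the over-attribution is in 1.1.
- **The share itself.** A reader might take one minus the start gap over 180 days (94-97% at midpoints) as the share that compares the two drugs. That also counts the 1.5 to 8 days when neither arm is on drug. The correct nominal share is 92-96%.
- **Time is not events.** Section 1.2 reports 24.7% mortality before discharge with a mean stay of 9.8 days, so risk may sit early. With a drug-only difference of about 0.1 patient per 60, a large early difference would be hard to put down to drug alone.
- **Masking.** A reader might infer that a real early bleeding excess would vanish by day 180. That needs the 1.70% in Step 4, which is simply the value that forces cancellation; no document supports it. At Table 3 rates masking is partial. Even the assumed doubling is only 0.6 vs 1.2 patients per arm of 60.
- **Other early safeguards.** There is a 30-day analysis, a day-14 scan, an item in 7.3 on the first 14 days, 24-hour reporting of symptomatic transformation to the DSMB (2.2), and a suspension rule at five such cases on apixaban (7.5.2). These matter for patient safety, but none gives a comparison by arm confined to the time before warfarin.
- **Limits of splitting the follow-up.** Comparing later events among those event-free at a cut is no longer a randomised comparison. The day-14 scan in TIA falls about a week after nominal warfarin start. Both points stand and shape the fix.

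**Conclusion.** The point holds in a limited form. Drug and start time change together, and at nominal start days both arms are on drug for about 92% (stroke) to 96% (TIA) of the 180 days, or 89-99% across the windows. The 30- and 180-day contrasts support conclusions about early apixaban versus later warfarin as regimens. They do not support the early-start claim as 1.1 words it.

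The likely size of the drug contribution is small at Table 3 rates. That rests on rates from trials that excluded recent stroke. It also sets aside scan-detected bleeding: 2.3.2.2 counts asymptomatic imaging findings, including more than three microbleeds, as hemorrhagic stroke, and the documents give no rate for these. The size of any masking is therefore unknown rather than shown to be large or negligible.

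A reader might also infer that the regimen comparison is invalid, or that an early-window result would isolate start time. Neither follows. A regimen comparison is a legitimate question for a pilot. Without an early-warfarin arm, the early window still compares early apixaban with mostly no anticoagulant. This is an inexpensive improvement in analysis and wording, not a design failure.

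**What to change.** 1. **Early-period comparison, in 8.1.2 and 8.1.3.** Compare the composite and intracranial hemorrhage by randomised arm, from randomisation to the nominal warfarin start of the stratum (day 7 TIA, day 14 stroke). Keep all randomised patients in the denominator and give the risk difference with 95% CI. Show later events by arm beside it, descriptively, and not as a randomised contrast among those event-free at the cut. Sections 7.1 and 8.1.2 list different components for the composite, so the table must state which definition it uses.
2. **Day-14 scan.** Report scan-detected hemorrhage by arm and stratum. In the stroke strata, treat it as a mostly pre-warfarin reading (warfarin day 9-19, scan day 14±3). In TIA, label it mixed.
3. **Wording of 1.1.** State that the 30- and 180-day results concern early apixaban versus later warfarin as regimens. Describe the early-period result as early apixaban versus mostly not yet anticoagulated, not as an isolated effect of start time.

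**Cost.** One extra table and a wording change, from events and scans already planned. There will be few early events and wide intervals. Some controls will have started warfarin before the cut, because the windows open on day 2 (TIA) and day 9 (stroke). The headline claim becomes narrower.

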### 1.2 Findings from pre-clinical and clinical studies

Currently, there are limited data regarding the early start of anticoagulation therapy following embolic stroke.

In the review of our local stroke database from October 2011 until December 2013, we examined the records of 336 small to medium stroke patients admitted to Tampa General Hospital with an ischemic stroke secondary to atrial fibrillation. The average age in our study population was  $75.3 \pm 1.83$  years of age. Stroke risk was similar to other AF groups in the literature, possessing an average CHADS2 score of  $2.6 \pm 0.26$  on admission; average CHA2DS2-VASc score was  $4.4 \pm 0.4$ . Average hospital stay was  $9.8 \pm 1.49$  days. We observed a  $24.7\% \pm 6.2\%$  mortality rate in our population prior to discharge. In addition, stroke survivors had a 5.1% recurrent non-fatal stroke risk. Patients with disabling or fatal

strokes were of a more advanced age than those who survived without severe disability ( $78.0 \pm 1.96$  years vs  $69.7 \pm 3.50$  years,  $p < 0.001$ ). Our data indicate that the risk of fatal to recurrent stroke is approximately 25 % with standard treatment (initiating anticoagulation approximately seven to fourteen days after signs and symptoms) for this group of patients.

The HAEST trial indicated that low molecular weight heparin results in a reduction in mortality and disability when used early (30 hours post stroke) in the treatment of ischemic stroke; however, this benefit is offset by an increased risk of intracranial hemorrhage

The previous studies on novel anticoagulation (NOAC) excluded subjects with a stroke/TIA within seven or less days; however, these randomized trials consistently demonstrated a lower risk of intracranial bleed compared to traditional anticoagulants ( see table 2).

[figure not shown]
ARISTOTLE followed a limited number of subjects (44) who suffered a stroke/TIA, between 7 and 14 days prior to randomization to treatment with either Apixaban or warfarin. There was only 1 subject in the warfarin group who suffered a major bleed. There were no recurrent stroke or systemic embolism in any of the 44 patients.

Recently investigators have reported the use of Dabigatran given within 24 hours of a TIA/minor stroke onset in a population of non-AF patients and have found it to demonstrate no significant increase in hemorrhagic transformation in this population.

Based on these limited data, we propose to examine the potential advantage of a treatment regimen of Apixaban at 0-3 days after TIA, 3-5 days after small ischemic stroke and 7-9 days after medium stroke in patients with atrial fibrillation

### 1.3 Name and Description of Investigational Product or Description of Intervention

Apixaban, a factor Xa (FXa) inhibitor, is chemically described as 1-(4-methoxyphenyl)-7-oxo-6-[4-(2-oxopiperidin-1-yl)phenyl]-4,5,6,7-tetrahydro-1H-pyrazolo[3,4-c]pyridine-3-carboxamide. Its molecular formula is C25H25N5O4, which corresponds to a molecular weight of 459.5. Apixaban has the following structural formula:

Apixaban is a white to pale-yellow powder. At physiological pH (1.2–6.8), apixaban does not ionize; its aqueous solubility across the physiological pH range is ~0.04 mg/mL.

This study is an open label, randomized, active controlled pilot study of Apixaban in subjects with NVAf who have, within 48 hours from signs and symptoms, been diagnosed with a TIA or a Small to Medium Ischemic Stroke as defined by the SACCO (see section 2.3).

In this study 120 patients with NVAf who have had a recent small or medium stroke or TIA (within 0-48 hours) will receive Apixaban twice a day for 180 days with drug initiation day 0-3 (TIA), day 3-5 (small stroke) or day 7-9 (medium stroke) respectively or receive standard of care warfarin starting at day 7±5 (TIA) or day 14 ±5 (small to medium ischemic stroke).

## **1.4 Selection of Drugs and Dosages**

### **1.4.1 Apixaban**

The dosage of Apixaban is based on the clinical findings of studies in human subjects and its FDA approved dosage for patients with nonvalvular atrial fibrillation. Patients will receive 5mg dosage twice a day or 2.5 mg if they have any 2 of the following characteristics:

- age ≥80 years
- body weight ≤60 kg
- serum creatinine ≥1.5 mg/dL

Coadministration with CYP3A4 and P-glycoprotein inhibitors: For patients receiving Apixaban 5 mg twice daily when Apixaban is coadministered with drugs that are strong dual inhibitors of cytochrome P450 3A4 (CYP3A4) and P-glycoprotein (P-gp) (e.g., ketoconazole, itraconazole, ritonavir, clarithromycin), the recommended dose is 2.5 mg twice daily [ patients already taking 2.5 mg twice daily, coadministration of Apixaban with strong dual inhibitors of CYP3A4 and P- glycoprotein should be avoided .

### **1.4.2 Warfarin**

Standard of care arm will be on Warfarin which will be locally sourced and commercial drug supply provided by Primary Investigator. See appendix 13.4 for dosing guidelines.

## **1.5 Compliance Statement**

This study will be conducted in full accordance with all applicable Institutional Policies of participating sites and Procedures and all applicable Federal and state laws and regulations including 45 CFR 46, 21 CFR Parts 50, 54, 56, 312, 314 and 812 and the Good Clinical Practice: Consolidated Guideline approved by the International Conference on Harmonisation (ICH). Any episode of noncompliance will be documented.

The investigators will perform the study in accordance with this protocol, will obtain consent, and will report adverse events in accordance with IRB Policies and Procedures and all federal requirements. Collection, recording, and reporting of data will be accurate and will ensure the privacy, health, and welfare of research subjects during and after the study.

## **2 STUDY GOVERNANCE**

### **2.1 Executive Committee**

The Executive Committee will be composed of a group of clinical experts responsible for ensuring that study design, execution and management are of the highest quality. The Executive Committee will monitor progress of study enrollment, make recommendations in collaboration with the sponsor based on the Stroke Adjudication Committee and DSMB Committee input, and oversee the presentation and publication of the trial results. The committee will convene regularly by teleconference and/or face-to-face meetings to discuss and report on the ongoing conduct of the study in collaboration with the sponsor. The chairman of the Executive Committee will serve as the third member to both the stroke adjudication and atrial fibrillation committees to meet consensus if necessary.

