## 2.2 Data and Safety Monitoring Board

The DSMB is responsible for safeguarding the interests of study participants, assessing the safety and efficacy of study procedures, and for monitoring the overall conduct of the study. The recommendations will be forwarded to the Executive Committee and the sponsor for final decision.

The DSMB is an independent group advisory to the executive board and is required to provide recommendations about continuing, and stopping the study. In addition, the DSMB is asked to make recommendations, as appropriate, about the benefit/risk ratio of procedures and participant burden

The DSMB will convene annually and at the milestones of 40 and 80 patients enrolled as well as at study conclusion to review safety data.

Notification of and referral for abnormal findings Data will be collected by the research team. Study data will be entered into the data collection forms or recorded electronically as they are collected during the study visit. The PIs will monitor all data for any inconsistencies or irregularity. If unanticipated adverse events or SAE of importance (symptomatic hemorrhagic transformation) are observed, they will be reported to the DSMB within 24 hours. All other AE's will be reported during scheduled meetings and to the IRB according to standard AE reporting policies. The Principal Investigator will forward all decisions to the regulatory authority as appropriate.

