## 2.3 Stroke Adjudication Committee (SACCO)

The Stroke Adjudication Committee will review and adjudicate all stroke endpoints. The committee will not be blinded to patient and study medication arm during the review of each stroke endpoint case.

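### Contested primary stroke events can be settled by the Executive Committee chairman, who knows the arm and has trial-leadership duties; the size of any bias is unknown

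*Combined protocol and SAP*

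**What the plan says.** Four statements in section 2 of the combined protocol and SAP bear on this.

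- **Who is the third adjudicator (2.1).** "The chairman of the Executive Committee will serve as the third member to both the stroke adjudication and atrial fibrillation committees". The role applies if it is needed to reach consensus.
- **What the Executive Committee does (2.1).** It is to "make recommendations in collaboration with the sponsor based on the Stroke Adjudication Committee and DSMB Committee input", and to "oversee the presentation and publication of the trial results".
- **Where DSMB advice goes (2.2).** "The recommendations will be forwarded to the Executive Committee and the sponsor for final decision". That advice covers continuing or stopping the study and the balance of benefit and risk.
- **How stroke events are judged (2.3).** "The Stroke Adjudication Committee will review and adjudicate all stroke endpoints". And: "The committee will not be blinded to patient and study medication arm during the review of each stroke endpoint case".

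The plan calls the DSMB independent (2.2). The readable text says nothing of the kind about the Executive Committee or its chairman. It gives no recusal rule, no voting rule and no way to identify cases that needed the third member. Section 2.3.1 (Adjudicators) is listed in the contents, but its text is not in the copy reviewed. The sensitivity analyses in 8.1.4 concern missing outcomes, not disputed ones.

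**The concern.** Adjudicators disagree on the cases where judgement matters most, such as a recurrence against progression of the index stroke, or a stroke death against another death. In those cases the plan brings in the head of the body that manages the trial, acts on DSMB advice and oversees the report. That person also knows the arm.

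This differs from the general lack of blinding in 2.3. If every case file were redacted, the chairman would still receive DSMB recommendations and still hold leadership duties. The lack of blinding makes the overlap worse, because the third member knows which arm a call would favour.

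The trial is open label and expects few primary events. If the result falls near the significance threshold, one or two contested calls could determine what is reported.

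**Working it through.** **No plan figure to reproduce.** The plan gives no number of expected disputes and no measure of fragility. The check therefore asks how often the final result would lie so close to P<0.05 that one call matters.

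**Inputs**
- 120 patients, 1:1 (8.1.5, 11.1): 60 per arm. The power calculation itself uses 50 per group.
- Control risk about 20% (8.1.5). Section 1.2 gives about 25%.
- Control-to-experimental risk ratio 2.30 (8.1.5): 0.20 / 2.30 = 0.087. This ratio serves only as a scenario. At 50 per group a standard two-proportion calculation gives it about 36% power, not the stated 80%, which is a separate matter.
- Threshold P<0.05 for the overall treatment effect (8.1.2), two-sided (8.1.5).
- Apixaban risks of 15% and 20% (no effect) are assumptions that show the range.

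**Single tables near the expected result.** Expected events are 60 × 0.20 = 12 and 60 × 0.087 ≈ 5. The test is the uncorrected chi-square, with z = (difference in proportions) / √[p(1−p) × 2/60] and p the pooled proportion.

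- 12 vs 5: p = 17/120 = 0.1417; z = 0.1167 / 0.0637 = 1.83; P = 0.067.
- 12 vs 4: p = 16/120 = 0.1333; z = 0.1333 / 0.0621 = 2.15; P = 0.032.
- 13 vs 5: p = 18/120 = 0.1500; z = 0.1333 / 0.0652 = 2.05; P = 0.041.

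One call moves the expected table across the threshold. One call further out does not: 12 vs 3 gives P = 0.013 and 12 vs 4 gives 0.032, both significant.

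**How often this happens.** Sum Binomial(60, control risk) × Binomial(60, apixaban risk) over every pair of event counts for which adding or removing one event in one arm changes whether P<0.05.

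| Control risk | Apixaban risk | Within one call |
|---|---|---|
| 20% | 8.7% | 26% |
| 20% | 10% | 23% |
| 20% | 15% | 11% |
| 20% | 20% (no effect) | 6% |
| 25% | 10.9% | 22% |

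Allowing two calls gives 49% at 20% vs 8.7% and 14% with no effect. At 50 per arm the one-call figures are 28% (20% vs 8.7%) and 8% (no effect). Fisher's exact test at 60 per arm and 20% vs 8.7% gives 24%. If the result is significant at 20% vs 8.7%, one call would undo it in about 30% of cases.

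**Which disputes change the outcome.** Sections 3.2 and 8.1.2 count fatal stroke, recurrent ischemic stroke and TIA. Section 7.1 counts fatal stroke, recurrent ischemic stroke and new hemorrhagic stroke.

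| Dispute | Changes outcome under 3.2 / 8.1.2 | Changes outcome under 7.1 |
|---|---|---|
| Recurrent ischemic stroke or no new event | yes | yes |
| Stroke death or other death (no earlier event) | yes | yes |
| TIA or no event | yes | no |
| TIA or ischemic stroke | no | yes |
| Non-fatal hemorrhagic stroke or no event | no | yes |
| Non-fatal hemorrhagic or ischemic stroke | yes | no |

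The first two rows matter under either composite, so the concern does not depend on which one is kept.

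**The case against.** **The figures measure fragility, not bias.** Any trial of this size is fragile whoever breaks ties. This stands. The percentages show when a contested call would matter, not that the chairman would call it wrongly. At 20% vs 8.7%, about 74% of results are not within one call.

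**A reader might infer that the chairman decides disputed endpoints by casting vote.** Section 2.1 says only that the chairman is third member, if needed for consensus. With 2.3.1 unavailable, the number of readers and the voting rule are unknown. The text supports that the chairman can settle a dispute, not that the chairman alone always does.

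**A reader might infer that the chairman sees accumulating results by arm, or has a personal stake.** Neither is documented. Section 2.2 says the DSMB reviews safety data and passes on recommendations, and 8.2 plans no interim analysis. The documented facts are the overlapping duties and the knowledge of each case's arm.

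**A reader might extend the point to the atrial fibrillation committee.** The chairman is its third member too, but no effect on the primary result is shown. Under 2.4 its diagnostic role comes before randomization, when no arm exists, and its end-of-study review feeds no analysis in section 8.

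**The larger weakness is that the whole stroke committee is unblinded.** This is true, and the third member acts only on disagreement. Independence of the tie-breaker is still a separate safeguard, and it is cheap.

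**This is a pilot.** Section 8.1.5 says the data will serve larger studies, which lowers the stakes. But 8.1.2 still tests the treatment effect at P<0.05, so the event calls still need protection.

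**A substitute from within the trial is not fully independent.** This stands in part: the substitute is still part of the trial. Removing the arm from the disputed file and having no DSMB material or Executive Committee seat removes the specific overlap described here.

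**Conclusion.** The concern holds as a governance weakness. Contested primary stroke events can be settled by a person who leads the committee that acts on DSMB recommendations and oversees publication, and who knows the arm.

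No size of bias can be stated, because the number of disputes, the voting rule and the content of the DSMB input are not given. The result is exposed only near the threshold: the chance of lying within one call is about 26% at 20% vs 8.7%, 11% at 20% vs 15%, and 6% with no effect.

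These figures assume 60 per arm with complete outcomes and a two-arm chi-square test. The planned logistic model with six subgroups could give somewhat different values. It would go too far to say that one reclassified event will reverse the conclusion. It can, if the result is borderline.

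**What to change.** 1. **Section 2.1, stroke endpoints only.** Replace the chairman as third member with a clinician already working in the trial who has no Executive Committee seat, receives no DSMB material and did not treat the patient. An investigator from another of the four sites would serve. State the voting rule, and align 2.3.1 with it.
2. **Section 2.3.** Provide that this third member reads the disputed file with arm information removed. That includes INR values and drug start dates: the schedule of procedures collects INR in the warfarin arm only after screening, and the two arms start on different days.
3. **Database.** Flag every case in which the third member was needed.
4. **Section 8.1.2.** Add a sensitivity analysis of the primary outcome with all flagged cases set first to event and then to non-event, and report the number flagged in each arm.
5. **Sections 3.2, 7.1 and 8.1.2.** Reconcile the composite, so that it is clear which disputes can change the outcome.

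The cost is small: short edits to the text, the substitute's time on the disputed cases, redaction of those files, and one extra analysis. The third reader is substituted, not added.
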